
Section	Original Text (Amendment 3.1, 21 December 2016)	Revised Text (Version 4, 10 May 2017)	Justification for Change
	
The propensity score quintile will be then be used as the stratification factor in the stratified log rank test to compare randomized OCA-treated subjects in the ITT population and historical controls (Overall Historical Control Population: both the UK-PBC Group and Global PBC Study Group databases) on the following outcomes:
 
 • Time to hepatocellular carcinoma 	
third-party statistician(s) will be separate and independent from the statistician(s) who will assess the success of matching and perform efficacy analyses.
 
The propensity score quintile will be then be used as the stratification factor in the stratified log rank test to compare randomized OCA-treated subjects in the ITT population and historical controls (Overall Historical Control Population: both the UK-PBC Group and Global PBC Study Group databases) on the following outcomes:
	

Section 13.1.9 Handling of Dropouts or Missing Data
	
Insertion
	
In addition, the same analyses for primary and key secondary endpoints based on ITT and PP populations will be performed to assess robustness of analysis results. During the conduct of the study, the DMC may recommend refining the missing data strategy to better address the observed pattern of missing data, based on blinded monitoring of the data.
	
Clarification of statistical analyses to address missing data.

Section 13.1.11 Examination of Subgroups
	
The primary and secondary efficacy endpoints will be analyzed for subject subgroups (eg, age, sex, and race) based on the ITT population.
 
Insertion
	
The primary and secondary efficacy endpoints will be analyzed for subject subgroups based on the ITT population.
 
The primary efficacy endpoint will also be assessed across the spectrum of PBC disease stage as defined by Rotterdam criteria (Kuiper 2009)
 
 • Early (normal albumin and normal bilirubin) 	
Added per Regulatory Authority request.

Section	Original Text (Amendment 3.1, 21 December 2016)	Revised Text (Version 4, 10 May 2017)	Justification for Change
		
 • Moderate (abnormal albumin or abnormal bilirubin) • Advanced (abnormal albumin and abnormal bilirubin) 
The primary efficacy endpoint will also be assessed for the following clinically relevant subpopulations.
 
 • Monotherapy in patients who are intolerant or non-responsive to UDCA • Elderly patients 
Assuming a strong correlation between biochemistry and clinical outcomes using the total study population (Section 13.1.5.1) is observed, we will further assess the biochemical improvement in relevant subpopulations as applicable (eg, Rotterdam disease severity and monotherapy) and estimate the reduction in risk of clinical outcomes associated with the biochemical improvement.
 
Additional details regarding statistical methods and subgroup definitions will be provided in the SAP.
	
This analysis will provide additional insight into the connection between surrogate endpoints and clinical outcome events allowing for evaluation of benefit in subpopulations for which the study is not powered.

Section 13.1.12 Continuous Monitoring and Interim Analyses
	
Both interim analyses will be pre-specified and will occur after accrual of 50% and 75% of clinical outcome events, respectively.
 
The DMC will review the available efficacy data in conjunction with detailed safety data and other relevant information to recommend continuation, modification, or cessation (for efficacy or utility) of the study beyond each interim analysis.
	
Both interim analyses will be pre-specified and will occur after accrual of 50% (64 events) and 75% (96 events) of clinical outcome events, respectively.
 
The DMC will review the available efficacy data in conjunction with detailed safety data and other relevant information to recommend continuation,
	
Added number of anticipated events.
 
Clarification

Section	Original Text (Amendment 3.1, 21 December 2016)	Revised Text (Version 4, 10 May 2017)	Justification for Change
		modification, or cessation (for efficacy) of the study beyond each interim analysis	

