
12.1.4.2 Reporting of Serious Adverse Event
	
In agreeing to the provisions of this protocol, the Investigator accepts all legal responsibilities for immediate reporting of SAEs to the medical monitor.
 
All SAEs occurring while subjects are receiving investigational product or are on an investigational product holiday (including Potential Clinical Outcome Events that qualify as serious) must be reported to the medical monitor immediately (ie, within 24 hours) after the Investigator identifies the SAE. SAEs are reported by entering the SAE data into the electronic data capture (EDC) system. Entering the SAE data into the EDC system will automatically notify the medical monitor of the event. In the event that the EDC system is inaccessible, an SAE may be reported by telephone or fax using a paper SAE Report form. If an SAE is reported by telephone or fax, an SAE Report form must also be completed in the EDC system as soon as the EDC system is accessible. At a minimum the following information should be provided at the time of the initial report:
 
subject number and initials, a description of the event, at least one criterion classifying the event as serious and the name and title of the reporting individual. Additionally, judgment of causality by the Investigator must be provided as soon as possible to ensure timely reporting to regulatory authorities by the Sponsor or designee(s). Following the initial report, any additional information obtained by the Investigator about the SAE must be reported promptly to the medical monitor. Any supporting source documentation should be faxed to
	
In agreeing to the provisions of this protocol, the Investigator accepts all legal responsibilities for immediate reporting of SAEs to the Sponsor. Immediate reporting implies within 24 hours of becoming aware of the occurrence of an SAE.
 
All SAEs must be reported to the Sponsor (including suspected liver-related clinical outcome events that qualify as serious).
 
SAEs are reported by entering the SAE data into the study-specific EDC system. Entering the SAE data into the EDC system will automatically notify the Sponsor of the event. In the event that the EDC system is inaccessible, an SAE may be reported by:
 
 • E-mail to the SAE email address: [contact] • Fax using a paper SAE report form: [contact] • [contact] 
If an SAE is reported by telephone or fax, an SAE Report form must also be completed in the EDC system as soon as the EDC system is accessible. At a minimum, the following information should be provided at the time of the initial report:
 
 • Subject number • Event term • At least 1 criterion classifying the event as serious • Name and title of the reporting individual • Causal relationship to the investigational product 
... The Sponsor will notify the appropriate regulatory agencies as well as all participating Investigators of investigational new drug (IND) Safety Reports/Expedited Safety Reports that occur during the study within the time frames required by each regulatory agency.
 
Following the initial report, any additional information obtained by the Investigator about the SAE must be
	
Updated guidance for reporting SAEs.

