
Section 12.1.5, Suspected Liver-related Clinical Outcome Events
	
Clinical Outcome Events (Appendix A) as well as Anticipated Events (Appendix B) will not undergo expeditious reporting.
	
12.1.5 Suspected Liver-Related Clinical Outcome Events
 
Specified liver-related clinical outcome events may, by definition (see Section 12.1.1.2) qualify as SAEs. The Sponsor must be notified of any SAEs within 24 hours of the site becoming aware of the event (see Section 12.1.4.2). The Sponsor is responsible for regulatory reporting of SAEs, including expeditious reporting of SUSARs, which are defined as SAEs that are considered related (definitely, probably, or possibly related) to the investigational product and considered unexpected as defined in the IB.
 
Given that the liver-related clinical outcome events could also meet the criteria of a SUSAR, please refer to Section 11.1.2.4.
 
The Sponsor will consider the following list of clinical outcome events (MedDRA preferred terms) to be disease related and exempt from expeditious regulatory reporting, but will continue to report them in a non-expeditious manner: death, end-stage liver disease (preferred term: chronic hepatic failure), liver transplant (preferred term: liver transplant), HCC (preferred term: hepatocellular carcinoma), variceal bleeding (preferred term: gastroesophageal variceal haemorrhage), hepatic encephalopathy (preferred term: hepatic encephalopathy), spontaneous bacterial and peritonitis (preferred term: peritonitis bacterial).
	
Updated section to account for events related to hepatic impairment.

Section	Original Text (Amendment 1.1, 12 November 2015)	Revised Text (Version 3, 07 September 2016)	Justification for Change

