	
 Endoscopy will be conducted at selected study sites where the device is available to assess for the presence of oesophageal varix/varices at baseline. 	
(where available), liver transplant, and death will be compared to historical controls.
 
 PK of OCA and its conjugates. Endoscopy will be conducted at all study sites where the device is available to assess for the presence of oesophageal varix/varices at baseline. 							

Section 12.1.3 Relationship of Adverse Events to Liver Biopsy
	
Insertion (new section)
	
The Investigator will document her/his opinion of relationship of an AE to liver biopsy using the criteria outlined in Table 9.
 
Table 9: Relationship of Adverse Events to Liver Biopsy
 
  
 Relation ship	Description	
   
 Related	A reaction that follows a reasonable temporal sequence from the liver biopsy; that follows a known or expected response pattern to the liver biopsy.	
 
 Not Related	Any event that does not meet the above criteria.	
  
	Relation ship	Description	Related	A reaction that follows a reasonable temporal sequence from the liver biopsy; that follows a known or expected response pattern to the liver biopsy.	Not Related	Any event that does not meet the above criteria.	
Added with the addition of liver biopsies for the confirmation of progression to cirrhosis.

Relation ship	Description								
Related	A reaction that follows a reasonable temporal sequence from the liver biopsy; that follows a known or expected response pattern to the liver biopsy.								
Not Related	Any event that does not meet the above criteria.								

Section 12.1.5.2 Reporting of Serious Adverse Events
	
[contact] If an SAE is reported by telephone or fax, an SAE Report form must also be completed in the EDC system as soon as the EDC system is accessible.
	
If an SAE is reported by email or fax, an SAE Report form must also be completed in the EDC system as soon as the EDC system is accessible.
	
Updated to align with modified standard safety procedures.
						

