12.1.1.5, Suspected Unexpected Serious Adverse Reactions	New section was added.	
A suspected unexpected serious adverse reaction (SUSAR) is defined as a suspected adverse reaction which is assessed as serious, causally related to the investigational product, and unexpected per the reference safety information (RSI) in the Investigator’s Brochure.
 
SUSARs are subject to expedited reporting. The Sponsor shall ensure that all relevant information about SUSARs that are fatal or life-threatening are recorded and reported as soon as possible to the relevant competent authorities (either directly or through the Eudravigilance Clinical Trials Module, as applicable), and to the Ethics Committees, no later than 7 days after knowledge by the Sponsor of such a case. Relevant follow-up information is subsequently communicated within an additional 8 days. All other SUSARs shall be reported to the competent authorities concerned (either directly or through the Eudravigilance Clinical Trials Module) and to the Ethics Committees concerned, within a maximum of 15 days of first knowledge by the Sponsor. Each competent authority shall ensure that all SUSARs to an investigational product which are brought to its attention are recorded. The Sponsor shall also inform all participating Investigators, as applicable to the local regulations.
	Updated AE reporting requirements for SUSARs

Section	Original Text (Amendment 5, 04 Jan 2018)	Revised Text (Version 6, 05 Nov 2019)	Justification for Change
14.1, Study Monitoring	The Investigator may exercise judgment in allowing the CRA access to particular sections of the subject's medical records if these are deemed irrelevant to the performance, observations or conduct of this study.	The Investigator may exercise judgment in allowing the CRA access to particular sections of the subject's medical records if these are deemed relevant to the performance, observations or conduct of this study.	Revision was made to correct a typographical error
17.3, Regulatory Documentation	
 • Form FDA 1572 	
 • Form FDA 1572 or equivalent form for the Investigator's region 	Revision was made for clarification purposes.

ADDENDUM 1 TO PROTOCOL 747-302

Netherlands-specific monitoring of subjects receiving CYP2D6 substrates with a narrow therapeutic index

PURPOSE

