Liver biopsies will generally be obtained from the right lobe of the liver as described in a study-specific histology manual. If the initial biopsy was obtained from the left lobe, then subsequent biopsies should be obtained from the left lobe, and vice versa.

All biopsy assessments, including screening and histology efficacy assessments, will be performed by study pathologist/central reader blinded to the treatment group assignment. The biopsies will be graded by a central reader using a pre-defined scoring system. Detailed information related to biopsy scoring will be provided to the central reader by the Sponsor in a study-specific histology manual.

Paired biopsies (Screening/Baseline biopsy and post-treatment [or EOT/EOS] biopsy) will be read by a central reader blinded to the treatment group assignment.

Biopsy Criteria for Progression to Cirrhosis

The following criteria will be used for adjudication of progression to cirrhosis:

- Persistent (ie, 2 consecutive measurements obtained at least 3 months apart) elevation in Fibroscan® TE >16.9 kPa, AND/OR
- Presence of any of the following:
 - Gastroesophageal varices
 - Ascites
 - Radiological evidence of cirrhosis (nodular liver or enlargement of portal vein and splenomegaly)
 - Combined low platelet count (<140,000/mm³), with any of the following criteria:
 - Persistent decrease in serum albumin, OR
 - Elevation in prothrombin time/international normalized ratio (not due to antithrombotic agent use), OR
 - Elevated total bilirubin >2x upper limit of normal

Transient Elastography

TE assessment will be performed at the investigational sites, where the device is available, using the Fibroscan instrument (Echosens, Paris, France), to assess liver fibrosis.

Noninvasive Scores of Liver Fibrosis

ELF score will be calculated using an algorithm that combines serum values of tissue inhibitor of metalloproteinases-1, procollagen type-3 N-terminal propeptide, and hyaluronic acid. Likewise, APRI score will be obtained from serum aspartate aminotransferase and platelet values.

ASSESSMENT OF SAFETY

Safety assessments will be performed as in Section 12 of the main protocol. In addition, the Investigator will document her/his opinion of the relationship of the adverse events (AEs) to liver biopsy using the criteria outlined in [Table 2](#).

Table 2: Relationship of Adverse Events to Liver Biopsy

Relationship	Description

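### The liver-biopsy causality table requires a known or expected pattern for Related, so on its natural reading a new kind of biopsy complication is labelled Not Related

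*Protocol*

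**What the plan says.** Section 12.1.3 was inserted with protocol Version 4 and appears in the change summaries of Appendices H and I. It instructs: "The Investigator will document her/his opinion of relationship of an AE to liver biopsy using the criteria outlined in Table 9". Table 9 has two rows. Related is "A reaction that follows a reasonable temporal sequence from the liver biopsy; that follows a known or expected response pattern to the liver biopsy". The other row, Not Related, is "Any event that does not meet the above criteria". There is no possible, probable or unknown level.

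Addendum 2, which defines the paired biopsy substudy, repeats the rule under Assessment of Safety: "the Investigator will document her/his opinion of the relationship of the adverse events (AEs) to liver biopsy using the criteria outlined in" its Table 2, whose two rows are worded as in Table 9. This is the addendum's own text and not an entry in a change log.

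For investigational product the protocol takes a different approach. The Version 3 text on suspected liver-related outcome events (Appendix F) describes SUSARs as serious events "considered related (definitely, probably, or possibly related) to the investigational product and considered unexpected as defined in the IB". Section 12.1.1.5, added in Version 6 (Appendix K), defines a SUSAR as a suspected reaction "assessed as serious, causally related to the investigational product, and unexpected per the reference safety information (RSI") of the Investigator's Brochure.

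**The concern.** Whether a procedure caused an event and whether that kind of event was foreseeable are separate questions. Table 9 makes the second a condition for answering yes to the first. A complication that appears soon after a biopsy, and that the investigator attributes to it, fails the definition of Related if nobody has described that pattern before. The investigator is asked for an opinion and then given criteria that can overrule it.

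The field exists to identify harms of the biopsy. Under this rule it records recognised complications and mislabels unrecognised ones. Any count or listing of biopsy-related events taken from it would understate what investigators believe the procedure caused, and would do so for the least familiar events.

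**Working it through.** No arithmetic decides this point. The check is to apply the table's own logic and compare it with the protocol's treatment of investigational product.

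**Step 1: the two clauses.** Let T mean that the event follows the biopsy with reasonable timing, and P mean that it fits a known or expected pattern. The clauses are joined by a semicolon, with neither *and* nor *or*. The label under each reading is:

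| T | P | Both clauses needed | Either clause enough |
|---|---|---|---|
| yes | yes | Related | Related |
| yes | no | **Not Related** | Related |
| no | yes | Not Related | Related |
| no | no | Not Related | Not Related |

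The case at issue is the second row: well timed and judged by the investigator to be caused by the biopsy, but of a pattern neither known nor expected.

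**Step 2: which reading is natural.** Two successive relative clauses describe one reaction, and the Not Related row refers to criteria in the plural. Both features point to the cumulative reading. The alternative is not workable either: timing alone would make any event soon after a biopsy Related, and pattern alone would make an event Related without plausible timing.

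**Step 3: exactly which events are affected.** The pattern test is *known or expected*. A known complication that was not expected in a particular subject still passes. Only an event that is neither known nor expected is mislabelled.

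**Step 4: comparison with investigational product.** The SUSAR definitions require an event to be related and also unexpected, so for the product the two attributes are judged separately and can occur together. Under the cumulative reading of the biopsy table, an event of a pattern neither known nor expected cannot be Related.

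**Step 5: is the text current?** The wording in Appendices H and I is the inserted wording. The change summaries for Versions 5 and 6 (Appendices J and K) list no change to Section 12.1.3. Addendum 2 carries the same table in its own text.

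**Step 6: scale.** The substudy plans about 45 subjects. Each has at most a baseline and one later biopsy, so the ceiling is 45 × 2 = 90. The actual number may be lower, because a biopsy taken within 6 months before Day 0 can serve as baseline. Confirmatory biopsies for suspected progression to cirrhosis in the main study add to this, but the documents give neither their number nor a rate of biopsy complications. The number of mislabelled events therefore cannot be computed; it is likely to be small.

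**The case against.** The strongest objection is that the semicolon leaves the logic open and that the investigator is asked for an opinion, so the table might be read as guidance. That ambiguity is real, and it is why the verdict depends on the natural reading. It does not rescue the table. The opinion is to be documented using the criteria, and a rule that sites can read in two ways needs rewording anyway.

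A second objection is that expectedness in a SUSAR is a test against the product's reference safety information, while the pattern clause is a plausibility test. The product-causality criteria themselves are not in the part of the protocol shown, nor is the current body of Section 12.1.3, and the later change summaries omit minor edits. This limits the comparison to what the SUSAR definitions show, namely that relatedness and expectedness are judged separately. Addendum 2 carries the finding without the body of Section 12.1.3.

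A reader might infer several stronger things that the documents do not support:

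- *That unfamiliar biopsy harms drop out of safety oversight.* They do not. The reporting text in Appendix F says "All SAEs must be reported to the Sponsor (including suspected liver-related clinical outcome events that qualify as serious"), whatever the biopsy label. Section 12.1.6 as revised in Version 4 describes DMC review of all safety and efficacy data at least quarterly, and Section 5.7 in Version 6 describes unblinded review of individual and aggregate data.
- *That a biopsy-related table feeding the DMC, ethics committees or consent is distorted.* No text shown describes such a table, and the statistical methods of Addendum 2 contain none.
- *That the biopsies carry no benefit for the subject.* This is too broad. Biopsy is one of the listed cirrhosis indicators for choosing the dosing regimen, and Addendum 2 says biopsies can inform severity and prognosis.
- *That every unexpected event is lost.* Known complications still qualify, as Step 3 shows.

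**Conclusion.** The point holds in a limited form. As worded, and on the natural cumulative reading, both tables give the wrong causality label to an event that the investigator attributes to the biopsy but whose pattern is neither known nor expected. The rule is stated in the documents and is not a detail left to the SAP.

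The consequence is confined to the biopsy-causality field and any summary built on it. Few events are likely to be affected, and no trial endpoint depends on the label. This is a low-priority correction, worth making because it is cheap.

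The conclusion rests on two assumptions: that the clauses are cumulative, and that no unlisted editorial change has altered Section 12.1.3. If the second fails, Table 2 of Addendum 2 still needs the correction.

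**What to change.** In Table 9 of Section 12.1.3, Table 2 of Addendum 2 and the CRF completion guide:

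- Define *Related* as an event that follows the biopsy with plausible timing and for which there is a reasonable possibility that the biopsy caused it, whether or not its pattern is known or expected.
- Define *Not Related* as an event for which there is no reasonable possibility that the biopsy caused it.
- Record expectedness as a separate item.

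The cost is wording in two identical tables and the guide, plus the separate expectedness item. A few more events may be listed as biopsy-related. No procedure, endpoint or sample size changes. Re-reviewing events already recorded is optional: it would need a retrospective causality assessment by investigators and is not part of this low-cost change.
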